6.30.2 Data Sources

For overall hospitalization costs, we will obtain complete hospitalization charges from HCA financial data, which do not include intervention costs. HCA has highly standardized financial records where charges for hospital beds, procedures, and various drugs and supplies are aggregated to produce a total hospitalization charge. Since hospital charges do not reflect true costs that hospitals incur, we will apply hospital cost-to-charge ratios obtained from HCA to obtain total hospitalization costs per admission.

Intervention costs, which will not be included in HCA charge data, will be determined as follows. We will measure the volume of supplies used multiplied by a standard unit cost. For all participating hospitals, we will collect unit-specific dispensed daily doses of mupirocin and chlorhexidine product. Mupirocin dispensing will be obtained from pharmacy data and chlorhexidine usage will be obtained from daily bathing compliance data obtained during the trial. Standard unit costs for each of these will be obtained from the manufacturer, publicly available data, or published sources. Chlorhexidine costs will be calculated as the incremental costs over the unit costs of common non-chlorhexidine bathing supplies. This will be done in two ways to account for the two most common chlorhexidine products on the market. First, we will calculate the incremental cost of disposable chlorhexidine-impregnated bathing cloths (as used in this trial) compared to disposable bathing cloths. Second, we will assume all bed baths are performed using basin baths and will calculate the incremental costs of adding generic liquid chlorhexidine to basins compared to routine soap and water basin baths. Finally, we will assess differences in the amount of unit-specific gown and glove use based upon supply chain data between arms and between baseline and intervention periods. This will account for potential cost-savings due to decreased transmission from the intervention.

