5.40.42 Data Creation

Since tracking of patient bathing is not routinely done in U.S. hospitals, a single nursing query was created to be completed once daily asking if a bath/shower was completed in the past 24 hours and whether the bath/shower involved chlorhexidine. If a bath/shower was not provided (regardless of use of chlorhexidine), the prompt requires a reason by providing common drop down options or free text entry. This bathing query was activated in March 2013 and is in use at all participating hospitals.

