HCA hospitals will be randomized into two study arms. Both arms will continue to conduct routine MRSA screening for high risk patients and will place MRSA+ patients in isolation precautions. The first arm will continue the routine policy of offering assisted or unassisted daily showers/bed baths with regular soap, and will agree not to institute components of the other arm for the duration of the study. In the second arm, all patients will be encouraged to shower or have a bed bath daily with chlorhexidine products. In addition, patients known to be MRSA+ will receive nasal mupirocin ointment twice a day for 5 days. We anticipate an average of 4 adult non-critical care units per hospital, for a total of 200+ units across the 54 hospitals.

For full recruitment details, see UH2 Aim 1. Participating hospitals will commit to having all eligible general adult non-critical care units participate in the trial. These are defined as step-down, medical, surgical, medical/surgical, and oncology units. Children <12 admitted to participating units will not receive the mupirocin protocol.

Hospital leadership will identify a trial champion for each unit as well as a liaison from their Infection Prevention Program and their Microbiology Laboratory. Participants agree to report all new initiatives slated to occur during the trial and to defer them if study investigators determine that they conflict with the trial. In addition, participating hospitals agree to collect bacterial isolates as specified in UH3 Aim 2 (Section 6.20).

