6.10.13 Limitations and Planned Solutions

This study has limitations. First, we require the enrollment of at least 50 HCA hospitals. While we believe this is possible due to our previous trial of 43 HCA hospitals, should enrollment drop unexpectedly to less than 50, we will pursue an elongation of the 18-month trial, (NOTE: intervention was extended to a 21-month trial in June 2015). Secondly, if hospital committee approvals for trial protocols are delayed, we will expand the phase-in period to a total of 3 months. We note that our prior trial completed phase-in within 30 days. Third, if decolonization is significantly better at preventing infection, we appreciate that we are unlikely to be able to distinguish between effects of chlorhexidine and the effects of active encouragement to bathe or shower. Nevertheless, the results of this study would reflect a real world intervention which would likely entail both processes.

Cluster randomization does not allow every question of interest to be addressed. It typically results in more misclassification of exposure than individual randomized controlled trials do, either because individual providers choose to use a non-recommended regimen for some patients, or they fail to adhere fully to the assigned regimen. To the extent that the frequency of failure is consistent with the level that occurs in usual clinical practice, these failures are part of the overall effectiveness measure. Thus, cluster randomization in inpatient systems may offer a relatively low-cost and broadly generalizable means to examine many of the priority topics for comparative effectiveness research. In addition, this study design does not allow for blinded assignment or implementation. Nevertheless, this reflects the pragmatic nature of our intervention and directly mirrors the design and implementation of hospital quality improvement initiatives.

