6.20.6 Limitations and Planned Solutions

If decolonization is successful, it is conceivable that isolation of MRSA and other bacterial pathogens may be substantially reduced, resulting in inadequate collection. In the event that this occurs, we will broaden the time window for isolate collection. Since our baseline period is 12-months and our intervention period is 18-months, (NOTE: intervention was extended to a 21-month trial in June 2015), the current plans to collect isolates for 9-months in each period still allows for additional collection time should it be necessary. We will monitor collection progress continually so that the collection period can be extended seamlessly, if this is needed.

6.30 Aim 3: Estimate the costs associated with the intervention (chlorhexidine + selective MRSA decolonization) and the attributable medical costs of healthcare associated infections in adult general inpatient units and infectious readmissions, in order to evaluate the potential for cost savings associated with the strategy of reducing bioburden to prevent infection.

Costs of healthcare associated infections (HAIs) have been studied mainly in academic medical centers.^{10 226 227 228 229 230} Estimates of HAI costs in community hospitals are needed since community hospitals represent the majority of inpatient care in the U.S., and costs may differ from academic hospitals.^{231 232 233} In addition, the cluster-randomized design affords an important and unique opportunity to assess the economic value of decolonization across a large number of hospitals. In particular, case mix differences between

hospitals can be closely adjusted for due to combination of several factors: 1) control group of hospitals with stratified randomization, 2) baseline data from each hospital, and 3) availability of individual patient adjusters from electronic health records and administrative data. In this aim, we will estimate the incremental hospital costs associated with the intervention and evaluate differences in total medical costs among patients with and without HAIs in the intervention and control arms. We will then estimate the net cost of medical care for the intervention and the control groups, adjusting for key health factors.

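### Aim 3 prices each chlorhexidine bath at its cost difference from an ordinary bath, which understates supply cost if encouragement raises bathing frequency

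*Protocol*

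**What the plan says.** The introduction to Aim 3 (Protocol 6.30) sets an incremental task: "we will estimate the incremental hospital costs associated with the intervention". Section 6.30.2 then gives the costing rule.

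- General method: "We will measure the volume of supplies used multiplied by a standard unit cost".
- Volume: "chlorhexidine usage will be obtained from daily bathing compliance data obtained during the trial".
- Unit price: "Chlorhexidine costs will be calculated as the incremental costs over the unit costs of common non-chlorhexidine bathing supplies".
- Two pricing scenarios. The first is "the incremental cost of disposable chlorhexidine-impregnated bathing cloths (as used in this trial) compared to disposable bathing cloths". The second assumes basin bathing throughout and compares a basin with generic liquid chlorhexidine against a soap-and-water basin.
- Intervention costs are stated to lie outside the hospital charge data.
- Gown and glove use is handled differently: the amounts used are compared between arms and between periods.

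On bathing itself, section 6.10.4 has the usual care arm continue to offer daily baths or showers with regular soap, while in the other arm "all patients will be encouraged to shower or have a bed bath daily with chlorhexidine products". Section 6.10.8 has nurses and bathing staff trained to give that encouragement. Section 6.10.13 concedes that "we are unlikely to be able to distinguish between effects of chlorhexidine and the effects of active encouragement to bathe or shower", and adds that real-world use would probably involve both. Section 5.40.42 describes the data source: "a single nursing query was created to be completed once daily asking if a bath/shower was completed in the past 24 hours", together with whether chlorhexidine was used. It has been active since March 2013 at all participating hospitals.

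**The concern.** Both pricing scenarios are one-for-one swaps, cloth for cloth or basin for basin. Each subtracts the cost of an ordinary bath from every chlorhexidine bath, as if that ordinary bath had been saved. A bath that would not otherwise have taken place saves no ordinary supplies, so its whole supply cost is incremental.

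The strategy under test has two parts, a product and a push to bathe daily. Any benefit from more frequent bathing enters the effect estimate. The plan, however, would charge each additional bath only the price difference. Because intervention costs are outside the charge data, nothing later in the plan restores the missing part. At stake are the intervention cost and the net cost of care that Aim 3 sets out to estimate.

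**Working it through.** There is no stated cost to reproduce, because the documents give no unit price and no bathing frequency. The check is therefore an identity, followed by a range under stated assumptions.

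**Notation.** b0 and b1 are baths per patient-day without and with the strategy. c0 and c1 are the supply costs of an ordinary and a chlorhexidine bath. For simplicity, all baths with the strategy are taken as chlorhexidine baths and all baths without it as ordinary. With a mix on either side the same shortfall results, provided chlorhexidine baths are counted as a change from background use.

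**Formulas.**

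1. Cost under 6.30.2: b1 × (c1 − c0).
2. Incremental supply cost: b1 × c1 − b0 × c0.
3. Shortfall, (2) minus (1): (b1 − b0) × c0.
4. Shortfall as a share of (2), with c1 = 1 and r = c0/c1: (b1 − b0) × r / (b1 − b0 × r).

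**Assumed inputs (none from the documents).** b0 0.50–0.75, b1 0.80–0.90, r 0.3–0.7. Share (4) rises with b1 and with r and falls with b0, so the first and third rows below are the extremes of this range.

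| b0 | b1 | r | Plan (1) | Incremental (2) | Shortfall | Share of (2) |
|---|---|---|---|---|---|---|
| 0.75 | 0.80 | 0.3 | 0.560 | 0.575 | 0.015 | 2.6% |
| 0.60 | 0.85 | 0.5 | 0.425 | 0.550 | 0.125 | 22.7% |
| 0.50 | 0.90 | 0.7 | 0.270 | 0.550 | 0.280 | 50.9% |

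Three further cases, also assumed, show the limits of the point.

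- Cheap ordinary supplies (r = 0.2, b0 = 0.60, b1 = 0.80): plan 0.80 × 0.8 = 0.64; incremental 0.80 − 0.12 = 0.68; shortfall 0.04, or 5.9%.
- No change in frequency (b0 = b1 = 0.80, r = 0.5): both give 0.40; shortfall zero.
- Fewer baths (b0 = 0.80, b1 = 0.70, r = 0.5): plan 0.35; incremental 0.70 − 0.40 = 0.30. The plan overstates cost by 0.05, or 17%.

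**The case against.** The strongest reply is that no rise in bathing has been shown. No section reports a bathing rate for either arm, and daily bathing is offered in usual care as well. Section 6.10.13 names encouragement as a possible source of effect but reports no increase. The interest in percent bathing daily as a balancing variable concerns differences between hospitals before randomization. This stands, and the point is conditional for that reason: more bathing is intended and plausible, not established.

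It can also be said that 6.30.2 does not write out its formula. The section does, however, give a volume, a unit price defined as a difference, and two one-for-one scenarios. Volume times price difference is the natural reading, so this is a stated rule and not merely missing detail.

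Three stronger readings are tempting, and the documents do not support them.

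- A reader might infer that the error always favours the intervention. Its sign depends on b1 − b0, as the last two cases in the working show.
- A reader might infer that the test for cost savings is biased. Section 6.30.3 models hospitalization cost, which comes from charges that exclude intervention costs, and does not say how supply cost enters that model or the savings per case averted.
- A reader might add staff minutes for every extra bath. Sections 1.4, 6.10.4 and 6.10.8 allow patients to bathe or shower themselves, and the query is not described as recording assistance. Restricting intervention cost to supplies is also a choice of costing perspective.

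**Conclusion.** The point holds in conditional form. The rule in 6.30.2 is correct only if chlorhexidine baths replace ordinary baths one for one. If bathing frequency rises as the strategy intends, incremental supply cost is understated by (b1 − b0) × c0.

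The size cannot be fixed from the documents. The range of about 3% to 51% rests wholly on the assumed rates and price ratios, and its upper end takes the extreme of all three at once. It is a share of incremental supply cost, not of net cost, and nothing here shows that a conclusion of Aim 3 would change.

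The reach is limited to the intervention-cost and net-cost estimates. Cost effectiveness is assigned to secondary manuscripts (6.10.6), and under 6.30.1 the cost analysis is done only after a significant benefit on the primary outcome. The primary analysis and its power are untouched. The correction is still worth making, because the error sits in a quantity that Aim 3 exists to estimate and the data to avoid it are being collected.

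**What to change.** Rewrite the chlorhexidine costing in 6.30.2 as follows.

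1. From the daily bathing query, count chlorhexidine and non-chlorhexidine baths per patient-day in both arms and both periods. Section 5.40.42 describes one entry a day, whereas 5.30.3 and 6.10.9 describe a response each shift. State one counting basis and use it throughout.
2. Multiply each count by its full unit cost, separately under the cloth and the basin scenario.
3. Take the arm-by-period difference in bathing cost per patient-day as the incremental bathing cost. This is the comparison of quantities that 6.30.2 already makes for gowns and gloves.
4. Report bathing frequency by arm and period alongside, so that readers can see whether the correction matters.

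Staff time is at most an optional scenario, with the share of assisted baths stated as an assumption. A check of ordinary bathing supplies against supply-chain records should not be promised without a further data request, since Table 4 in 5.40.2 lists only chlorhexidine under that source.

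The cost is one rewritten paragraph and a little more analysis, with no change to trial conduct. If bathing does rise, the stated intervention cost will be somewhat higher.

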6.30.3 Analysis

We will use an analytic approach similar to our primary outcome of MDRO organism from a clinical or screening culture attributed to a participating non-ICU unit, with the exception that we will model will the outcome of hospitalization cost. Rather than proportional hazard models with shared frailties, we will use generalized linear mixed models to evaluate whether the Decolonization Arm is associated with significant cost-savings when accounting for clustering by hospital. Since cost data are typically quite skewed, data transformation may be required to assure adequate fit of the outcome distribution. Models will be chosen to fit the distribution: negative binomial models, or possibly, normal distributions after log transformation, for example. Either approach reduces the impact of large outliers typical in cost data. Model terms will include arm, trial period (baseline vs intervention), their interaction, unit type (step down, medical, surgical, etc.), and demographic and comorbidity variables. The assessment of whether outcomes in one arm are significantly different from the other will be determined by the significance of this interaction term, which assesses whether the mean cost difference between the baseline and intervention period differs significantly between the two arms. If significant, we will calculate the mean cost savings per case averted.

We will additionally perform a sensitivity analysis to account for potential mortality effects on total hospitalization costs. To do this, we will assign a large fixed hospitalization cost to all deaths and assess if the model still predicts cost savings.

6.30.5 Limitations and Planned Solutions

This analysis is limited by the inability to account for all potential confounders that may put one individual at higher risk for hospitalization cost. However, cluster randomization is a major asset for distributing both known and unknown confounders. The availability of data from the baseline period is an additional strength, since each hospital's patient population additionally serves as its own control.

6.40 Overall ABATE Infection Trial Summary

Healthcare-associated infections (HAI) continue to produce high morbidity, mortality, and over \$6 billion dollars of annual healthcare costs in the U.S.. Most infections arise from bacterial flora, which overcome host defenses during vulnerable times such as hospitalization. Gains in HAI reduction due to decolonization regimens have been demonstrated for ICU settings, but evidence is lacking about the effectiveness of such strategies in non-ICU settings, where the majority of HAIs occur, and where medical care, risk of infection, patient-to-patient interactions, pathogen transmission, and bathing practices differ considerably from ICU settings. This 50-hospital cluster-randomized trial will critically assess whether daily bathing with chlorhexidine and intranasal mupirocin for MRSA carriers should become standard practice for 40 million patients hospitalized each year in the United States alone. Alternatively, it will suggest that tailored strategies distinct from those effective in ICU settings are needed to reduce the >1 million HAIs that occur each year in non-critical care settings.

This trial will also illustrate the strengths of an underused model of clinical effectiveness research that quickly and efficiently allows robust randomized clinical trials to be embedded into the normal delivery of health care, using the organizational and informatics strengths of a large hospital system.

6.50 UH3 Trial Intervention Phase Milestones and Timeline

We summarize our milestones and timeline for the trial intervention phase in **Table 15**. We will work closely with the NIH Collaboratory Coordinating Center during all aspects of the trial, including study design, implementation, data extraction, quality control processes, and confirmation of study outcomes. Our lead investigators will actively participate in the HCS Research Collaboratory Steering Committee, and members of our investigative team will actively participate in HCS Research Collaboratory Work Groups to align goals, activities, and deliverables to improve the conduct of pragmatic clinical trials during usual medical care.

Table 15. UH 3 Trial Intervention Phase - Annual Milestones and Timeline

UH3 Milestone	Details / Purpose	Trial Phase Timeline			
		Y1	Y2	Y3	Y4
Aim 1: Decolonization Trial					
1. Clinical Trial Registration	Registration with Clinicaltrials.gov	x			
2. Randomization of Hospitals	Cluster randomization using hospitals as the cluster	x			
3. Standardized Nursing Protocol	Approval of assigned protocol through requisite hospital committees	x			
4. Computer Based Training	All frontline staff with confirmed training on trial protocol, by arm	x			
5. Product Compatibility	Substitution of skin products incompatible with chlorhexidine	x			
6. Stocking Product	Supply chain infrastructure ensures product availability	x			
7. On Site Bathing Training	All hospitals randomized to decolonization receive on site training	x			
8. Coaching Calls	Monthly arm-specific coaching calls*	x			
9. Compliance Reports	Routine capture and reporting of protocol compliance	x	x		
10. Bathing Observations	Quarterly bathing observations to confirm process	x	x		
11. Data from Central Warehouse	Routine data pulls for needed trial data elements	x	x	x	
12. Data Cleaning Routines	Establish cleaning routines for serial data pulls	x	x	x	
13. Final Data Pull	Complete final data pulls from centralized data warehouse			x	
14. Analytic Data Set (Primary)	Establish final analytic dataset (Primary Manuscript)			x	
15. Statistical Analysis (Primary)	Statistical analysis of trial outcomes (Primary Manuscript)			x	
16. Analytic Data Set (Secondary)	Establish final analytic dataset (Secondary Manuscripts)				x
17. Statistical Analysis (Secondary)	Statistical analysis of trial outcomes (Secondary Manuscripts)				x
18. Dissemination of Results	Presentations, manuscript preparation and submission			x	x
Aim 2: Resistance					
1. Strain Collection	Strain collection occurs during baseline and intervention periods	x	x		
2. Resistance Testing	Testing strains for mupirocin and chlorhexidine resistance			x	
3. Analytic Data Set	Establish final analytic dataset after cleaning, quality checks			x	x
4. Statistical Analysis	Statistical analysis of resistance outcomes				x
5. Dissemination of Results	Presentations, manuscript preparation and submission				x
Aim 3: Cost Effectiveness					

1. Data Pull for Charges	Total hospitalization charges and intervention costs acquired			x	
2. Literature Review	Common cost-to-charge ratios and usual product costs assessed			x	
3. Analytic Data Set	Establish final analytic dataset after cleaning, quality checks				x
4. Statistical Analysis	Statistical analysis of cost outcomes				x
5. Dissemination of Results	Presentations, manuscript preparation and submission				x
Resource/Software Products					
1. Decolonization Toolkit	Trial related materials to implement decolonization in hospitals	x			
2. Computer Training Modules	Computer-based training module for decolonization	x			
3. E-Documentation Modules	MEDITECH programs for nursing bathing documentation	x			
4. Product Compatibility Charts	Chlorhexidine compatibility charts for skin care products	x			
5. Podcasts and Webinar Content	Podcasts and PowerPoint presentations for decolonization	x			
6. Strain Collection Toolkit	Detailed directions for trial strain collection	x			
7. Randomization Software	SAS/R software for stratified cluster randomization		x		
8. Microbiology Mining Programs	SAS programs for parsing and analyzing microbiology results		x	x	
9. Bacterial Strain Bank	Large strain bank of MRSA and gram negative bacterial pathogens			x	x
10. Analytic Programs	SAS programs for analysis of cluster-randomized trials				x
11. Publications	Publication of all trial, resistance, and cost outcomes				x

Bibliography and References Cited

- ¹ Klevens RM, Edwards JR, Richards CL Jr, et al. Estimating health care-associated infections and deaths in U.S. hospitals, 2002. *Public Health Rep* 2007; 122:160-166.
- ² European Centre for Disease Prevention and Control. Annual epidemiological report on communicable diseases in Europe 2008. Report on the state of communicable diseases in the EU and EEA/EFTA countries. Copenhagen: European Centre for Disease Prevention and Control, 2008.
